#### **7.4.3.2 Evaluation**

The time scale considered is the month.

Time to treatment failure will be plotted using the Kaplan Meier estimator. Median times and rates at different temporalities will be calculated, along with their 95% confidence intervals.

### **7.4.1 Better response to treatment**

#### **7.4.1.1 Definition**

The best response to treatment will be assessed according to mRECIST criteria.

#### **7.4.1.2 Evaluation**

The best response to treatment (CR, PR, S, P) will be calculated and described using standard descriptive statistics. It will be described according to the investigator.

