Note: The time between collection and freezing (at -20°C) of plasma should not exceed 1 hour.

Complete the sample census form (present in the study investigator's binder) and send it by [contact]) or by email ([contact]) to the FFCD as soon as the 4 sampling times have been completed.

The repatriation of the samples to the CRB (biological resource center) EPIGENETEC of the FFCD, will be done at the end of the study by a specialized carrier.

Imaging for correlation with VEGF assay

Perform a cone beam CT or CT scan without injection after the 1^{ière} HEC.

An anonymized copy should be sent to the FFCD. A blank CD ROM is provided in the patient's CRF.

X. CENTRALIZED READING OF MRI AND CT

Responses will be evaluated according to the mRECIST version 1.1 (primary endpoint) and EASL (secondary endpoint) criteria (Appendices 4 and 5) and will be reviewed by a panel of independent radiologists who will confirm responses and dates of tumor progression or recurrence once all study examinations have been retrieved.

For this purpose, an **anonymized copy on CD ROM** (present in each observation book) **of each morphological evaluation until progression** (even if beyond 6 months) (MRI) is to be made. **The copies will be sent to the CRGA of the FFCD for centralized review.**

XI. MANAGEMENT OF SERIOUS ADVERSE EVENTS (SIA)

1. Security assessment parameters

Safety will be assessed by evaluating the general and clinical condition of patients and by collecting events occurring between visits during consultations. Toxicities will be assessed using the NCI-CTC-AE version 4.0 toxicity scale (see Appendix 6).

In case of an emergency, the patient, his family or his physician should call the investigator to warn of an event.

2. Definitions

a. Adverse Event (AE)

An adverse event is a harmful occurrence in a person who is a subject of biomedical research, whether or not the occurrence is related to the research or the product being investigated.

All adverse events will be recorded in the observation book on the pages provided.

b. Serious Adverse Event (SAE)

A serious adverse event (SAE) is considered to be any event:

- Resulting in death,
- Life-threatening,
- Leading to hospitalization or prolonged hospitalization,
- Causing permanent disability or severe temporary incapacity,
- Causing a birth defect, fetal malformation or abortion,
- Medically significant.

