- The rate of patients in objective response** (complete response or partial response) at 6 months according to mRECIST criteria and evaluated by the investigator.
- The rate of patients in objective response** (complete response or partial response) at 6 months according to EASL criteria assessed by the investigator and in centralized review.

- Time to treatment failure

It is defined as the time interval between the date of inclusion and the date of protocol treatment failure. Death, progression, and any discontinuation of protocol treatment (regardless of cause) are considered treatment failures.

Patients alive without failure will be censored at the date of the last 6-month morphological evaluation.

- The best response according to the mRECIST criteria

- Progression-free survival

It is defined as the time interval between the date of inclusion and the date of 1st progression according to mRECIST criteria (assessed in centralized review) or death (regardless of cause).

Patients living without progression will be censored at the date of last news.

- Overall survival

It is defined as the time interval between the date of inclusion and the date of death (regardless of cause) or the date of last news for living patients.

- Tolerance of the treatment

Toxicities will be evaluated by the NCI-CTC v4.0 criteria. They will be described according to their grade in terms of number of toxicities and number of patients who experienced the toxicity.

- Quality of life (QLQ-C30 questionnaires and its HCC18 module specific to HCC)

XII.3 Calculation of the number of subjects needed

The assumptions are:

- H0: A proportion of patients with an objective response at 6 months of 25% or less is not acceptable
- H1: A proportion of patients with an objective response at 6 months of more than 25% would demonstrate the effectiveness of the treatment. A rate of 40% is hoped for.

Using a 2-stage Fleming design (Fleming, 1982) with a one-sided alpha risk of 5% and power of 90%, it is necessary to include **86 treated and evaluable patients**.

At the 1^{ère} stage: 43 patients will be included

- If 10 or fewer patients have an objective response, the trial will be stopped for futility (H1 rejection)
- If 18 or more patients have an objective response, the trial will be stopped for efficacy (rejection of H0)

If not, we will go to 2^{ème} step including 43 additional patients

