#### **4.3 Randomization and blinding**

The trial is open-label. There is no randomization in this trial.

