## 7.3 Evaluation of primary endpoint efficacy

#### Population CP

### 7.3.1 Definition of primary efficacy endpoint

The primary endpoint is the objective response rate 6 months after inclusion. Objective response (complete and partial response) is defined according to mRECIST criteria and based on centralized review (or on the investigator's opinion if review is not possible).

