### **7.4.2 OR patient rate according to EASL**

#### **7.4.2.1 Definition**

The rate of objective response (complete and partial response) 6 months after inclusion will also be evaluated according to EASL criteria in centralized review and according to the investigator.

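### Best mRECIST response is planned from the investigator's reading only, although the SAP gives every other response endpoint, and progression-free survival, a centralized version

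*SAP*

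**What the plan says.** The SAP numbers two sections 7.4.1. The second one covers best response. Its definition reads "The best response to treatment will be assessed according to mRECIST criteria" and names no assessor. Its evaluation paragraph supplies one: "It will be described according to the investigator". No centralized version is listed.

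Protocol XII.2.2 lists the endpoint as "The best response according to the mRECIST criteria" and also names no assessor.

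Protocol section X says that mRECIST and EASL responses "will be reviewed by a panel of independent radiologists who will confirm responses and dates of tumor progression or recurrence". The material sent to the panel is an anonymized copy "of each morphological evaluation until progression", including evaluations beyond 6 months.

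Elsewhere the SAP uses the central reading. The primary endpoint (7.3.1) is "based on centralized review (or on the investigator's opinion if review is not possible". The EASL rate (7.4.2.1) "will also be evaluated according to EASL criteria in centralized review and according to the investigator". Progression-free survival takes its progression date from centralized review. On masking, SAP 4.3 states: "The trial is open-label. There is no randomization in this trial".

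**The concern.** Best response takes the most favourable of several readings per patient. The protocol plans an MRI 4 to 6 weeks after each of up to four sessions, plus the 6-month scan. In an open-label single-arm trial, one generous local reading at any of these scans can set a patient's category. This is the response endpoint on which an independent reading helps most, and it is the only one without one.

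What is at stake is how a published figure is read. With one reader and one population, and with the 6-month scan among the candidates, the best-response rate cannot fall below the 6-month rate. With an investigator best response beside a mainly central primary rate, that ordering is not guaranteed, and the two figures come from sources with different protection against reader bias.

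**Working it through.** The plan gives no figure for this point, so the check sets the texts side by side. The sample size and the two-stage decision rule do not use best response.

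**Step 1. Assessor by endpoint**

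| Endpoint | Protocol XII.2 | SAP |
|---|---|---|
| 6-month mRECIST response (primary) | Central | Central; investigator if review is not possible (7.3.1) |
| 6-month mRECIST response (secondary) | Investigator | Investigator (first 7.4.1); its central counterpart is the primary endpoint |
| 6-month EASL response | Investigator and central | Both (7.4.2.1) |
| Progression-free survival | Central | Central |
| Best mRECIST response | Not named | Investigator only (second 7.4.1) |

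The SAP keeps the protocol's assessor wherever one is named, adding only the fallback for the primary endpoint. The last row is the one the protocol left open, and the only response endpoint with no central version.

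**Step 2. Are the central readings available?** Section X has the panel review responses on copies of all morphological evaluations up to progression. Centrally assessed progression-free survival also requires the panel to follow each patient's scans to first progression. The inputs for a central best response are therefore already planned, with no extra scans or readers.

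**Step 3. What can be separated under the present SAP?**
- Time effect, same reader: investigator best response against investigator 6-month response.
- Reader effect, same time: central against investigator mRECIST response at 6 months.
- Not measured: reader disagreement at scans other than the 6-month one, any of which may set the best response.

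**Step 4. Scale.** SAP 4.6.1 gives 46 patients included and 44 evaluable for the primary endpoint. The best-response section names no population. Protocol XII.4 places efficacy analyses on the evaluable patients, which makes 44 the more natural denominator, but this remains an assumption.
- n = 44: 1/44 = 0.0227, about 2.3 percentage points per patient.
- n = 46: 1/46 = 0.0217, about 2.2 percentage points per patient.

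A patient counts here only if the two readings differ on responder status (complete or partial response against neither). A disagreement between complete and partial response changes the category table but not the combined rate.

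**Step 5. Size of the difference.** This needs the net number of such disagreements. The documents give no agreement data between investigator and panel, so it cannot be calculated.

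**The case against.** The strongest reply is that the SAP breaks no rule. The protocol names assessors for the other response endpoints and for progression-free survival but not for best response. The SAP fills that gap and states the assessor, so a reader will know the source. Section X describes a reading process and does not say that best response must be reported from it. The endpoint is descriptive, with no test, threshold or decision attached. All of this stands. It limits the point to an unexplained departure from the SAP's own pattern, but it gives no reason to leave out readings that will exist.

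Four stronger readings are tempting, and the documents do not support them:
- **That a blinded reading is being discarded.** The panel is called independent and the copies anonymized. Nothing says that the panel is blinded to the investigator's result, and its task of confirming responses leaves that open.
- **That reader and time effects cannot be separated.** The investigator 6-month rate allows both comparisons in Step 3. Only disagreement at the other scans is left unmeasured.
- **That the investigator figure is too high by some number of points.** Neither the size nor the direction of any difference is given. Multiplying an assumed over-call rate by 44 would only restate the assumption.
- **That the assessor was chosen because of the results.** The SAP already reports the interim result of 22 responders among 44, but the documents do not show when or why the assessor for best response was chosen.

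One practical objection also stands. SAP 7.3.1 foresees that central review may not be possible for some patients, so a central best response needs a rule for them.

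**Conclusion.** The point holds as a minor, optional improvement. Best mRECIST response is the only response endpoint in the SAP without a centralized version, although the central readings needed for it are planned and no reason is given for leaving it out. This is an inconsistency within the SAP and not a contradiction of the protocol.

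The primary conclusion is unaffected: the decision to stop for efficacy rests on the 6-month endpoint. The difference between investigator and central best response is unknown. Its scale is about 2.3 points per patient with discordant responder status, assuming a denominator of 44. That the central readings suffice rests on section X being carried out as written, with all evaluations up to progression reaching the panel.

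**What to change.** In the evaluation paragraph of the SAP's best-response section (the second 7.4.1.2):
- report best mRECIST response by centralized review as well as by the investigator;
- name one population and use it for both;
- add a cross-table of the two classifications;
- where central review is not possible, apply the convention of SAP 7.3.1 (investigator's opinion) and report how many patients this concerns. Show them separately in the cross-table, because they agree by construction.

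If the sponsor prefers the investigator version alone, one sentence should give the reason.

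The cost is one extra summary and one cross-table from readings already planned. No new scans, readers or patients are needed, and the primary analysis does not change.

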### **7.4.2 Progression-free survival**

#### **7.4.2.1 Definition**

It is defined as the time between the date of inclusion and the date of first progression assessed by centralized review, or the date of death (whatever the cause). Patients alive without progression will be censored at the date of last evaluation.

Patients for whom no evaluation is available will be censored at inclusion date + 1 day.

#### **7.4.2.2 Evaluation**

The time scale considered will be the month.

Progression-free survival will be plotted using the Kaplan Meier estimator. Median progression-free survival and survival rates at different time points will be calculated, along with their 95% confidence intervals.

### **7.4.3 Overall survival**

#### **7.4.3.1 Definition**

It is defined as the time interval between the date of inclusion and the date of death (all causes). Living patients will be censored at the date of last news.

#### **7.4.3.2 Evaluation**

The time scale considered will be the month.

Overall survival will be plotted using the Kaplan Meier estimator. Median survival and survival rates at different time points will be calculated, along with their 95% confidence intervals.

## **7.5 Tolerance assessment**

### **Population SP**

#### **7.5.1 Chemoembolization**

Chemoembolization will be described by :

- The number of chemoembolizations performed per patient
- Chemoembolization territories
- HEC postponements (number of postponements, number of days postponed, cause)
- Complications during the procedure
- Post-treatment complications.

#### **7.5.2 Toxicities**

Toxicities (graded according to NCI-CTC v 4.0) will be described by :

- Total number of patients by maximum grade of toxicity (grade 1-2-3-4-5);
- The number of patients and the maximum toxicity grade reached (grade 1-2-3-4-5) by SOC and toxicity type;
- Total number of patients by maximum grade of toxicity, grouped by grade (grade 1-2 and grade 3-4-5);
- The number of patients and the maximum toxicity grade reached by grouping grades (grade 1-2 and grade 3-4-5) by SOC and toxicity type.

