Statistical methods	
The assumptions are:
 
 • H0: a proportion of patients with an objective response at 6 months of 25% or less is not acceptable • H1: A proportion of patients with an objective response at 6 months of more than 25% would show the effectiveness of the treatment. A rate of 40% is hoped for. 
Using a 2-stage Fleming design (Fleming, 1982) with a one-sided alpha risk of 5% and power of 90%, it is necessary to include 86 treated and evaluable patients.
 
At the 1^{ère} stage: 43 patients will be included
 
 - If 10 or fewer patients have an objective response, the trial will be stopped for futility (H1 rejection) - If 18 or more patients have an objective response, the trial will be stopped for efficacy (rejection of H0) 
If not, we will go to 2^{ème} step and include 43 additional patients.
 
If 29 or more patients have an objective response, the treatment will be declared effective (rejection of H0)
 
Taking into account a rate of 5% of lost to follow-up or not assessable, 91 patients will be included. The decision rules will be adapted based on the number of evaluable patients actually included.

Biological studies	Analysis of VEGF level by ELISA technique and progastrin level then correlation with tumor and non-tumor liver volumes.
Number of subjects needed	91
Planned study period	
Rate of 10 patients per month (1 patient per month per center - 10 centers)
 
Expected start date of inclusions: September 2014.
 
Expected completion date of inclusions (stage 2): July 2016
 
Expected completion of study: January 2020

EXAMINATION AND FOLLOW-UP SCHEDULE

	BEFORE TREATMENT	DURING TREATMENT with CHE			AFTER 6 MONTHS (patient follow-up)	
	Within 28 days before 1 ^{ière} HEC and before inclusion	Before each HEC	After each HEC	At 6 months after inclusion	1 ^{ière} year every 3 months	2 ^{ième} year every 6 months
Clinical and biological informed consent	X					
CLINICAL EXAMINATION						
Weight, height, pain assessment (VAS)	X	X			X	
General status WHO	X	X			X	
Child-Pugh if associated cirrhosis and BCLC score	X					
Quality of life (QLQ-C30 and HCC-18)	X	X				
Description of the disease and medical history	X	X				
Toxicity assessment (NCI-CTC v4.0)			X	X		
MORPHOLOGICAL EXAMINATIONS*** (IN FRENCH ONLY)						
Hepatic MRI	X		X	X	X****	X****
Ultrasound of the liver					X****	X****

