CAT scan for extra-hepatic evaluation	X		X (in case of contraindication to MRI)	X	X (thoracic every 6 months)	X (thoracic)
Portal Doppler if thrombosis is suspected on imaging	X	X (recommended)				
ECG	X					
Evaluation of left FEV	X					
BIOLOGICAL ASSESSMENT						
Biological check-up	X*	X**			X (liver test)	X (liver test)
AFP marker	X				X	X
Serology (HBsAg, anti-HBs, anti-HCV)	X					
Pregnancy test (within 7 days of inclusion)	X					
BIOLOGICAL STUDY						
Samples: 2 EDTA tubes of blood then centrifugation for aliquoting of 4 cryotubes of plasma and freezing at -20°C then -80°C		X (D0, D1, D2 and D3 of 1 ^{ière} HEC)				
IMAGERY*** : CT cone beam or CT scan without injection during the procedure						

* Complete biological check-up: CBC/platelets, PT, AST, ALT, alkaline phosphatases, GGT, bilirubin (total, free and conjugated), factor V, blood ionogram, creatinine, albumin, blood sugar, blood calcium

** Biological check-up before each HEC: CBC, platelets, blood ionogram, creatinine, albumin, ASAT, ALAT, PAL, GGT, total and conjugated bilirubin, PT

*** : An anonymized copy of the imaging is to be sent to the FFCD for centralized review

**** : hepatic MRI (or CT) / ultrasound of the liver by a trained operator alternating every 3 months for 2 years

I. OBJECTIVES OF THE TRIAL

I.1 Main objective

The objective of this non-randomized phase II study is to evaluate the objective response rate (complete and partial response) at 6 months, assessed according to the mRECIST criteria in centralized review.

I.2 Secondary objectives

The secondary objectives of this study are to evaluate:

- The investigator-assessed 6-month objective response rate (mRECIST)
- Time to treatment failure
- The best answer according to mRECIST
- Objective response rate at 6 months (EASL)
- Progression-free survival
- Overall survival
- Tolerance of the treatment
- Quality of life (QLQ-C30 questionnaires and its HCC18 module specific to HCC)

II. PATIENT SELECTION

II.1 Inclusion criteria

- Histologically proven HCC or according to EASL/Barcelona criteria for nodules ≥ 1 cm
- Tumor not amenable to curative treatment (liver transplantation, surgical resection or percutaneous destruction)
- Measurable targets according to mRECIST v1.1 criteria
- Preserved liver function (in case of cirrhosis, Child-Pugh A or B7 without history of edemato-ascitic decompensation)
- Tumor classified as BCLC A or B without portal or extrahepatic invasion or C if WHO= 1

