- Digestive disorders: nausea, vomiting, diarrhea
- Stomatitis, esophagitis
- Elevated liver enzymes and bilirubin in 20-30% of cases
- Skin rash
- Acute heart rhythm disturbances, acute or late heart failure (rare before a cumulative dose of 93 mg/m²)
- Red coloration of the urine 24 to 48 hours after treatment.

As with other DNA altering anticancer agents, myelodysplastic syndromes and acute myeloid leukemias have been observed after combination therapy with anthracycline.

In case of idarubicin-related effects, no dose adjustment of idarubicin for loading the microbeads is planned. The chemoembolization session is then postponed or cancelled.

VII. MONITORING DURING AND AFTER TREATMENT

VII.1 Before each HEC

- Complete clinical examination: weight, vital signs, WHO general condition (which should be 0 or 1), pain assessment (VAS)
- Biological work-up: CBC/platelets, blood ionogram, creatinine, albumin, transaminases (AST, ALT), alkaline phosphatases (ALP), GGT, total and conjugated bilirubin, PT
- Adverse event evaluations of previous HECs according to NCI CTC version 4.0
- Quality of life questionnaires (QLQ-C30 and its module HCC18)

Prior to the session, the investigator should ensure that the patient has adequate hepatic and hematological function:

- Bilirubin ≤ 1.5 mg/dL, PNN $\geq 1,000/\text{mm}^3$, platelets $\geq 50,000/\text{mm}^3$, creatinine level $\leq 150 \mu\text{mol/L}$
- Hepatopoietic flow, thrombosis is considered significant if it involves at least 3 segments. The procedure is then contraindicated. A Doppler is strongly recommended before the embolization sessions to ensure that the procedure can be performed. It is recommended to evaluate these criteria according to the habits of the center.

For patients participating in the translational study: blood sampling for translational study (see paragraph IX)

VII.2 After each HEC

Hepatic MRI (or CT scan in case of contraindication to MRI) will be performed 4 to 6 weeks after each chemoembolization to assess their effectiveness.

Assessment imaging at 6 months from the date of inclusion MUST be performed regardless of the time of last HEC to assess the primary endpoint of the study.

Target measurements will be done according to mRECIST v1.1 to assess the primary endpoint of the study and according to EASL criteria to assess the secondary endpoint (Appendices 4 and 5).

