## 6.5 Baseline definition

Baseline measurements are the last measurements taken at inclusion. In the event of missing data, the last measurement taken before the first treatment is used.

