### 7.1.3 Clinical features

#### Population ITT

The following characteristics at inclusion will be described:

- WHO general status (0 vs 1)
- BMI (kg/m^2)
- BCLC (A vs B vs C)
- Child-Pugh (A vs B7 vs B8 vs B9 vs no cirrhosis)
- Pain assessment
- Medical history :
  - Etiology of hepatopathy (hepatitis B, hepatitis C, alcohol, hemochromatosis, metabolic disease, other)
  - Presence of associated cirrhosis (Yes vs. No)
  - Presence of metabolic syndrome (Yes vs. No)

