### 7.1.4 Biological characteristics

#### Population ITT

The following characteristics at inclusion will be described:

- Wafers (x10 /mm^3)
- PNN (/mm^3),
- Creatinine (μmol/L)
- Albumin (g/L)
- P rate (%)
- Hemoglobin (g/dL),
- Total bilirubin (Number of x normal)
- Conjugated bilirubin (number of x normal)
- AST (Number of x normal)
- ALAT (Number of x normal)
- PAL (Number of x normal)
- GGT (Number of x normal)
- AFP (Number of x normal)
- Blood glucose (g/L)
- V factor (%)
- Sodium (g/L)

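### SAP 7.5.2 summarises toxicity only as the worst absolute grade, with no reference to the patient's pre-treatment grade, so abnormalities present at entry can be counted as toxicity

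*SAP*

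**What the plan says.** SAP 7.5.2 lists four toxicity summaries, all built on the maximum NCI-CTC v4.0 grade per patient: overall and by organ class and type, each with grades 1 to 5 separate and then grouped as 1-2 and 3-5. The most detailed is "The number of patients and the maximum toxicity grade reached (grade 1-2-3-4-5) by SOC and toxicity type". Protocol XII.2.2 describes the same endpoint as counts: "They will be described according to their grade in terms of number of toxicities and number of patients who experienced the toxicity".

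SAP 6.5 does define a baseline: "Baseline measurements are the last measurements taken at inclusion". A later value taken before the first treatment is used only if the inclusion value is missing. SAP 7.1.4 describes the inclusion laboratory values for the whole group, with the enzymes as multiples of normal, for example "AST (Number of x normal". The toxicity section uses neither.

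Protocol II.1 admits patients with platelets from 50,000/mm³, neutrophils from 1,000/mm³ and "Preserved liver function (in case of cirrhosis, Child-Pugh A or B7 without history of edemato-ascitic decompensation". It sets no limit for transaminases. Protocol VII.1 requires bilirubin of at most 1.5 mg/dL before each session.

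**The concern.** Low platelets and raised liver enzymes can come from the underlying liver disease or from the treatment. Protocol VI.1 names transient thrombocytopenia, liver dysfunction and raised transaminases among the expected effects of the procedure. Protocol VI.2 lists for idarubicin "Elevated liver enzymes and bilirubin in 20-30% of cases". Disease and treatment signals can therefore land in the same rows of the same table.

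A control arm would show the background rate. This trial has none, and Protocol XIII states that it aims to confirm the safety of the beads. The same section says that the randomised trial of doxorubicin-loaded beads can serve for comparison on safety. If the counts include abnormalities that were there before treatment, haematological and hepatic rates are too high. A worst absolute grade also hides real worsening: a patient who moves from grade 1 to grade 2 looks the same as one who entered at grade 2 and stayed there.

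Child-Pugh does not fill the gap. The schedule ticks "Child-Pugh if associated cirrhosis and BCLC score" only before treatment, so the laboratory values are the main per-patient view of change in liver function.

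**Working it through.** The documents give no figure on this point, so there is none to reproduce. The check is mainly textual.

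**1. Is there a rule anywhere that limits the count to new or worsened events?**

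| Place | What it fixes | Baseline rule? |
|---|---|---|
| SAP 7.5.2 | Maximum grade per patient | No |
| SAP 5.1.3 | Which patients count (at least one chemoembolization) | No |
| SAP 6.5 | Defines baseline | Not linked to toxicity |
| Protocol XI.2 | An adverse event is any harmful occurrence, related or not | No onset or worsening needed |
| Protocol XII.2.2 | Counts by grade | No |
| Schedule; Protocol VII.1 | Toxicity assessed after each session and at 6 months; before a session, events from earlier sessions are reviewed | Fixes when, not what |

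**2. Can abnormal values be present before session 1?** Yes. The entry limits above allow low platelets and neutrophils and any transaminase value. Bilirubin is bounded by the pre-session cap, and Protocol II.2 excludes severe hepatic insufficiency, so the room is smaller for bilirubin.

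**3. Are the data for a baseline grade collected?** Yes. Protocol III requires a full panel before inclusion. Protocol VII.1 requires blood count, platelets, AST, ALT, bilirubin, albumin and PT before each session, including the first.

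**4. How large could the effect be?** This can only be illustrated. All inputs are assumptions:

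- N = 46, the number included at the interim (SAP 4.6.1). The size of the safety population is not stated.
- q = share of patients with a graded value of a given test before treatment.
- r = share of the remaining patients who develop that toxicity after treatment.
- s = share of unchanged baseline abnormalities that are recorded as toxicities.

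Patients reported = N × [s × q + (1 − q) × r]. With s = 0 only new onsets appear. The gap between s = 1 and s = 0 is N × q.

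| q | r | s = 0 | s = 1 | Gap |
|---|---|---|---|---|
| 10% | 10% | 4.1 | 8.7 | 4.6 |
| 30% | 10% | 3.2 | 17.0 | 13.8 |
| 50% | 10% | 2.3 | 25.3 | 23.0 |
| 10% | 30% | 12.4 | 17.0 | 4.6 |
| 30% | 30% | 9.7 | 23.5 | 13.8 |
| 50% | 30% | 6.9 | 29.9 | 23.0 |

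Example, q = 30% and r = 10%: with s = 1, 46 × (0.30 + 0.70 × 0.10) = 46 × 0.37 = 17.0; with s = 0, 46 × 0.07 = 3.2.

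The gap is an upper bound for each q. Patients abnormal at baseline who then worsen are genuine toxicities under either rule, and the formula leaves them out of the s = 0 column. The documents fix neither q nor s, so the true excess may be zero.

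**The case against.** The strongest reply is that toxicity is collected as post-treatment events. The schedule marks no toxicity assessment before treatment, Protocol VII.1 speaks of events from previous sessions, and Protocol XI.2 has events recorded in the observation book. Investigators may well leave out a platelet count that has not moved. This stands as a reason not to claim that the tables will be wrong. It does not close the gap: a persistent low count can still be graded at a post-session visit, and without a written rule practice can differ between centers.

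It is also fair that SAP 7.1.4 shows the group's starting values. That helps a reader, but it cannot link one patient's worst grade to that patient's own start. Toxicity is a descriptive secondary endpoint with no decision rule in the SAP, and over-counting would be conservative for a safety claim. Both points limit the severity. Neither helps to identify real worsening.

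Three stronger readings are tempting and are not supported:

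- A reader might infer that the population is largely cirrhotic. Cirrhosis is conditional in the entry criteria and is tabulated as "Presence of associated cirrhosis (Yes vs. No"; no share is given.
- A reader might infer that existing disease is in fact reported as toxicity. The documents do not say whether grades come from laboratory values or from investigator entries.
- A reader might take the 20-30% figure in Protocol VI.2 as a rate of abnormality at entry. It describes expected effects of idarubicin.

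**Conclusion.** The point holds as a gap in the analysis rule. SAP 7.5.2 counts the maximum absolute grade, nothing else in either document restricts it to new or worsened events, and entry allows abnormal values of the very tests that the treatment is expected to affect. Pre-existing abnormalities can therefore be counted as toxicity. The number of patients affected is unknown. The counts in the working are illustrations that depend on assumed shares and on how investigators record events.

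The consequence is confined to the safety description, chiefly the haematological and hepatic rows. The primary endpoint, the sample size and the decision to stop for efficacy are not touched. This is a cheap and worthwhile improvement, not a fault that undermines the trial.

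**What to change.** In SAP 7.5.2:

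- Make the main toxicity summary the events that start, or worsen in grade, after the first session.
- For this purpose, derive the baseline grade from the last value before session 1: the Protocol VII.1 panel, or the inclusion value if that panel is missing. This reverses the order in SAP 6.5 for safety only and should be stated as such.
- Add shift tables from baseline grade to worst grade for platelets, neutrophils, AST, ALT, bilirubin, albumin and PT. If the toxicity scale does not grade a test in the units recorded, tabulate its change in value.
- Keep the present absolute-grade tables as supportive.

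The cost is SAP wording and some programming; no new data are needed. There are three limits. Baseline grades must be derived from recorded values, because no toxicity grading is scheduled before treatment. Scheduled panels fall before each session, and the later follow-up in Protocol VII.3 lists liver tests but no blood count, so the worst grade after the last session may have to come from the recorded toxicity grades, above all for platelets and neutrophils. Finally, a patient who starts just above a grade boundary and crosses it with a small fall still counts as worsened under this rule; the shift table at least shows where that patient began.
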